7.2 INCLUSION CRITERIA

I 01. Age ≥ 18 .

I 02. Patients must have a known diagnosis of multiple myeloma with evidence of measurable disease, as defined below:

- Serum M-protein ≥ 1 g/dL (≥ 0.5 g/dL in case of IgA disease),

AND/OR

- Urine M-protein ≥ 200 mg/24 hours,

OR

- In the absence of measurable M-protein, serum immunoglobulin free light chain ≥ 10 mg/dL, and abnormal serum immunoglobulin kappa lambda free light chain ratio (< 0.26 or > 1.65).

I 03. Patients must have received prior treatment with an IMiD (for ≥ 2 cycles or ≥ 2 months of treatment) and a proteasome inhibitor (for ≥ 2 cycles or ≥ 2 months of treatment).

I 04. Patients must have received at least 3 prior lines of therapy (Note: Induction therapy and stem cell transplant \pm maintenance will be considered as one line).

I 05. Patients, must have achieved MR or better with any anti-myeloma therapy (ie, primary refractory disease is not eligible).

I 06. Patients understand and have signed the Written Informed Consent form and are willing and able to comply with the requirements of the trial.

I 07. Anti-CD38 refractory cohort only: Patients who received anti-CD38 mAb within 6 months before study entry and had disease progression while on treatment or within 60 days after the last treatment.

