13.4.1 Demographics and baseline characteristics

Demographic and baseline characteristics (including age, gender, race, ethnicity, ECOG performance status), medical or surgical history, MM characteristics at diagnosis and at study entry will be summarized with descriptive statistics for the safety population in Phase 1 or ITT population in Phase 2.

Prior anti-myeloma therapies

The following parameters regarding prior anticancer will be summarized:

- Prior anticancer treatment: number of prior lines (defined in [Appendix E](#)), number of prior regimen, main anticancer treatments (Alkylating agents, proteasome inhibitors, immunomodulators, monoclonal antibodies).
- Refractory status to main anticancer treatments.
- Description of last regimen given prior to study entry:
 - Time from completion of last regimen of treatment to first study treatment (months),
 - Main treatments,
 - Best response to last regimen,
 - Duration of last regimen of therapy,
 - Refractory status as defined above.
- Prior transplant: number (%) of patients with transplant, type of transplant, time from last transplant to first study treatment (months).
- Prior surgery: number (%) of patients with prior surgery, type of surgery and time from last surgery to first study treatment (months).

- Prior radiotherapy: number (%) of patients with prior radiotherapy, intent and time from last radiotherapy to first study treatment (months).

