A line of therapy consists of ≥ 1 complete cycle of a single agent, a regimen consisting of a combination of several drugs, or a planned sequential therapy of various regimens (eg, 3-6 cycles of initial therapy with bortezomib-dexamethasone followed by stem cell transplantation consolidation, and lenalidomide maintenance is considered 1 line).

New line of Therapy

A treatment is considered a new line of therapy if any 1 of the following 3 conditions are met:

1. **Start of a new line of treatment after discontinuation of a previous line.** If a treatment regimen is discontinued for any reason and a different regimen is started, it should be considered a new line of therapy. A regimen is considered to have been discontinued if all the drugs in that given regimen have been stopped. A regimen is not considered to have been discontinued if some of the drugs of the regimen, but not all, have been discontinued.

The reasons for discontinuation, addition, substitution, or SCT do not influence how lines are counted. It is recognized that reasons for change may include end of planned therapy, toxicity, progression, lack of response, inadequate response.

2. **The unplanned addition or substitution of 1 or more drugs in an existing regimen.** Unplanned addition of a new drug or switching to a different drug (or combination of drugs) due to any reason is considered a new line of therapy.
3. **Stem cell transplantation (SCT):** In patients undergoing >1 SCT, except in the case of a planned tandem SCT with a predefined interval (such as 3 months), each SCT (autologous or allogeneic) should be considered a new line of therapy regardless of whether the conditioning regimen used is the same or different. It is recommended that data on type of SCT also be captured.

Planned tandem SCT is considered 1 line. Planned induction and/or consolidation, maintenance with any SCT (frontline, relapse, autologous or allogeneic) is considered 1 line.

Interruptions and dose modifications

- If a regimen is interrupted or discontinued for any reason and the same drug or combination is restarted without any other intervening regimen, then it should be counted as a single line.
- However, if a regimen is interrupted or discontinued for any reason, and then restarted at a later time point but 1 or more other regimens were administered in between, or the regimen is modified through the addition of 1 or more agents, then it should be counted as 2 lines.

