Prior anti-myeloma treatments are collected by regimens on eCRF. A line of therapy consists of \geq 1 complete cycle of a single agent, a regimen consisting of a combination of several drugs, or a planned sequential therapy of various regimens (eg, 3-6 cycles of initial therapy with bortezomib-dexamethasone followed by stem cell transplantation consolidation, and lenalidomide maintenance is considered 1 line; Amended protocol Version 3.0, Appendix E). An algorithm will be used to determine number of prior lines: a new line of therapy starts if:

- There is an evidence of progression/relapse. OR,
- A planned course of therapy is modified as a result of toxicity, progression/relapse, lack of response, inadequate response, or any other reasons indicative of incomplete treatment or change of plan.

The following analysis of prior anticancer treatment will be performed.

- Prior anticancer treatments:
 - Number of prior lines (quantitatively and by category: 1, 2... 7 and \geq 8),
 - Number of prior regimens (quantitatively and by category: 1, 2... 7 and \geq 8),

- Main anticancer treatments:
 - Alkylating agents: including cyclophosphamide, melphalan, bendamustine, cisplatin,
 - Proteasome inhibitors: including bortezomib, carfilzomib, ixazomib,
 - Immunomodulators: including lenalidomide, thalidomide, pomalidomide,
 - Histone deacetylase (HDAC) inhibitors: panobinostat,
 - Corticosteroids: dexamethasone, prednisone,
 - Anthracyclines,
 - Vinca alkaloids,
 - Monoclonal antibodies: including elotuzumab, daratumumab and other anti CD38 agents,
- Description of last regimen prior to study entry:
 - Time from completion of last regimen of treatment to reference date (months),
 - Main treatments,
 - Best response to last regimen,
 - Duration of last regimen of therapy (months).

In addition, the refractory status to main anticancer treatment (as listed above) and refractory status of the last prior anticancer treatment received before enrollment will be derived. A patient is considered to be refractory if any of the following conditions are met:

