d Only for analysis based on investigator assessment, BOR will be PD for patients without response assessment who received 1 cycle of treatment and died due to PD or had symptomatic deterioration within 30 days of last study treatment administration.

e Unconfirmed PD, unless PD is based on radiological assessment that does not need confirmation.

BOR=best overall response; sCR=stringent complete response; CR=complete response; MR=minor response; NE=not evaluable; PD=progressive disease; PR=partial response; SD=stable disease; VGPR=very good partial response.

Figure 1 - Determination of BOR when disease assessments are performed after new anti-myeloma therapies are started or performed after the cutoff date

DA= Disease assessment – PR=Partial response; PD= progressive disease.

① DA3 and subsequent are excluded from the BOR determination. BOR will be MR.

② DA2 will be used to confirm PD since PD was first documented at DA1 before initiation of a new anti-myeloma therapy. BOR will be PD.

③ DA5 and subsequent will be excluded from the analysis since performed after the cutoff date. BOR will be MR.

Subgroup analyses of BOR will be performed for the variables listed in [Table 4](#).

Table 4 - List of variables for subgroup analyses

Variable	Description
Age	<70 years vs ≥70 years
Gender	Male vs female
Number of previous lines of therapy	≤3 vs >3
ISS staging at study entry	I vs II vs III
High risk cytogenetic	Yes vs No
Baseline creatinine clearance (MDRD)	<60 ml/min/1.73m ² vs ≥60 ml/min/1.73m ²
Refractory to IMiD	Yes vs No
Refractory to PI	Yes vs No
Refractory to IMiD and PI	Yes vs No
Refractory to daratumumab	Yes vs No
Baseline PD-L1 level	≥50% vs <50%

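### The SAP counts prior lines of therapy by a rule that conflicts with protocol Appendix E and does not declare the change, so the prior-lines table and the descriptive ≤3 versus >3 subgroup can carry wrong counts

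*SAP*

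**What the plan says.** Protocol 13.4.1 lists, among the baseline summaries, "number of prior lines (defined in" Appendix E). Appendix E counts by regimen. A different regimen after the previous one has stopped is a new line whatever the cause: "The reasons for discontinuation, addition, substitution, or SCT do not influence how lines are counted". Unplanned addition or substitution of a drug is also a new line, and so is a further stem cell transplant (SCT) outside a planned tandem. Planned sequential therapy is one line. Three things do not start a line:

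- Stopping part of a combination: "A regimen is not considered to have been discontinued if some of the drugs of the regimen, but not all, have been discontinued".
- Changing the dose of the same regimen.
- Resuming the same treatment: "If a regimen is interrupted or discontinued for any reason and the same drug or combination is restarted without any other intervening regimen", the whole is a single line.

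SAP 2.1.1 repeats the Appendix E definition of a line and then gives its own algorithm with two triggers. The first is "There is an evidence of progression/relapse". The second is that "A planned course of therapy is modified as a result of toxicity, progression/relapse, lack of response, inadequate response", or for any other reason that points to incomplete treatment or a change of plan. None of the Appendix E exceptions is carried over. SAP 1.5, which records changes to the protocol's statistical section, mentions only the move from first dose date to randomization date.

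The count has two uses in the SAP. It fills the baseline table (categories 1 to 7 and ≥8), and "Number of previous lines of therapy" is a Table 4 subgroup variable, cut at ≤3 versus >3. That subgroup is applied to ORR and best overall response (SAP 2.4.4.1) and to PFS (SAP 2.1.3.2).

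**The concern.** The protocol names one definition and the SAP programs another. Appendix E sets the reason for a change aside, whereas the SAP's second trigger depends on it. The SAP's first trigger needs only progression or relapse, with no change of drugs.

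The subgroup cut makes a one-line error visible. Inclusion criterion I 04 says "Patients must have received at least 3 prior lines of therapy", so if enrolment follows it the ≤3 group should hold only patients with exactly three lines. One extra line moves such a patient into >3. The subgroup is meant to separate the least from the more heavily pretreated patients, and the wrong patients would then be compared. A reader of the report would also assume that the baseline table follows the protocol definition, because no departure is declared.

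**Working it through.** The plan gives no figure for this point, so the check sets the two rules side by side and applies them to constructed histories.

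**Step 1. Which events start a line**

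| Event | Appendix E | SAP 2.1.1 |
|---|---|---|
| Progression, then a different regimen | +1 | +1 |
| Relapse, same regimen restarted, nothing in between | 0 | +1 (first trigger) |
| One drug of a combination dropped for toxicity | 0 | +1 if recorded as a modified or new regimen, otherwise 0 |
| Planned course completed, then a different unplanned regimen without progression | +1 | 0 if a completed course is not a modified one; +1 if the switch is read as a change of plan |

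**Step 2. Count for a patient**

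Lines = 1 (first treatment) + the sum of the later events.

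| History after the first line | Appendix E | SAP |
|---|---|---|
| Two progressions, each followed by a new regimen | 1+1+1 = 3 | 1+1+1 = 3 |
| The same, then relapse and restart of the same regimen | 1+1+1+0 = 3 (≤3) | 1+1+1+1 = 4 (>3) |
| Two progressions with new regimens, then one drug dropped for toxicity | 1+1+1+0 = 3 (≤3) | 4 (>3) or 3, depending on the eCRF record |
| Two progressions with new regimens, then a completed course followed by a different unplanned regimen | 1+1+1+1 = 4 (>3) | 3 (≤3) or 4, depending on the reading |
| One progression with a new regimen, then relapse and restart of the same regimen | 1+1+0 = 2 | 1+1+1 = 3 |

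The first row shows that histories made only of progression followed by a new regimen agree. The second and fifth rows differ under the plain wording of both texts. The third and fourth differ only under one of two possible readings.

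**Step 3. Does the count reach the primary analysis?**

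SAP 2.4.4.1 tests ORR by Fisher's exact test with a Hochberg adjustment in the randomized population, and prior lines do not enter. As a check on the sample size, exact enumeration of the one-sided Fisher test with 35 versus 35 patients, 20% versus 50% and alpha 0.05 gives a power of 79.1%, which matches the stated 79%. That calculation does not use prior lines either.

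**The case against.** The best defence is that the SAP's wording is wide and works on regimen records.

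- **Completed course, then a different regimen.** The second trigger ends with a catch-all for a change of plan, and the SAP limits a multi-regimen line to planned sequences. An unplanned different regimen can fairly be read as a change of plan. Under-counting is therefore possible but arguable.
- **One drug dropped.** The SAP says prior treatments are collected by regimen. If the site keeps a single record when one drug stops, there may be nothing for the algorithm to split. The eCRF is not among the documents, so this over-count is conditional.
- **Same regimen restarted after relapse.** Neither argument helps here. The first trigger is met, and Appendix E says the opposite.
- **Protocol version.** The SAP refers to amended protocol version 3. The change summaries for amendments 04 to 06 list no change to Appendix E, so this does not explain the difference.

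A reader might go further and infer that the SAP rule lets ineligible patients appear to meet I 04, or eligible ones appear to fail it. The documents do not support that as a consequence of the plan. Eligibility is judged at screening, I 04 carries its own counting note and does not cite Appendix E, and major deviations are settled by data review (protocol 13.2.2). No section uses the SAP count to check I 04.

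**Conclusion.** The conflict is real and undeclared. Its firm core is the restart of the same regimen after relapse, which the SAP counts as two lines and Appendix E as one. Over-counting after a dropped drug depends on the eCRF, and under-counting after a completed course depends on how the change-of-plan wording is read.

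The size is one line per event. It matters most at the 3/4 cut, where a patient with three Appendix E lines can be placed in >3. The effect falls on the baseline prior-lines table and on one of the eleven variables in Table 4. The ORR and best overall response subgroup results are descriptive (SAP 2.4.4.1), and no hypothesis is tested on secondary endpoints (SAP 2.4.4.2). Who is enrolled, the primary test and the power are unaffected.

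The documents give no frequency for these histories, so the number of miscounted patients cannot be calculated. Any assumed percentage would also count every patient with a discrepancy, rather than the fewer who cross the cut. This is an alignment that should be made because it is cheap and the protocol already names the rule; it does not threaten the trial's main conclusion.

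**What to change.** Replace the two-trigger algorithm in SAP 2.1.1 with the full Appendix E rules.

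- **New line:** a different regimen started after all drugs of the previous one have been stopped, for any reason; an unplanned addition or substitution of a drug; or a further SCT that is not part of a planned tandem.
- **Still one line:** planned sequential therapy such as induction, SCT, consolidation and maintenance. This must be stated, because the first rule on its own would split it.
- **Not a new line:** stopping only some drugs of a regimen, changing the dose, or restarting the same regimen with no other regimen in between.

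Use this count for both the baseline table and the Table 4 subgroup. If the sponsor prefers its own algorithm, SAP 1.5 should declare and justify it, and the report should state how many patients change category between the two rules.

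The cost is some reprogramming and medical review of treatment histories. Protocol 12.2 already collects drug names, transplant dates, progression date, best response and reason for discontinuation. It lists no explicit field for whether a change was planned, so unclear cases need medical review.

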Appendix F Definition of relapsed and refractory myeloma

Refractory Myeloma:

Refractory myeloma is defined as disease that is non-responsive (failure to achieve minimal response or develops PD while on therapy) while on primary or salvage therapy, or progresses within 60 days of last therapy. There are 2 categories of refractory myeloma.

- Relapsed and refractory myeloma: Relapsed and refractory myeloma is defined as disease that is non-responsive while on salvage therapy or progresses within 60 days of last therapy in patients who have achieved minimal response or better at some point previously to then progressing in their disease course.
- Primary refractory myeloma: refractory myeloma is defined as disease that is non-responsive in patients who have never achieved minimal response or better with any therapy. It includes patients who never achieve MR or better in whom there is no significant change in M protein and no evidence of clinical progression; as well as primary refractory, progressive disease where patients meet criteria for true progressive disease.

Relapsed myeloma

Relapsed myeloma is defined as previously treated myeloma which progresses and requires the initiation of salvage therapy but does not meet the criteria for either primary refractory myeloma or relapsed and refractory myeloma.

(Adapted from Rajkumar VS, Harousseau J-L, et al. Consensus recommendations for the uniform reporting of clinical trials: report of the International Myeloma Workshop Consensus Panel 1. Blood. 2011;117(18):4691-95.)

Appendix G Recommended dose modification or discontinuation and supportive care guidelines for specific cemiplimab drug related adverse events

Colitis Adverse Event Management

Colitis events CTCAE v4.03	Isatuximab Dose Management	Cemiplimab Dose Management	Actions and Guidelines	Diagnostic considerations

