Progression date and anticancer treatment end date are complete and progression date is within (\leq) 60 days of anticancer treatment end date (Progression date - anticancer treatment end date \leq 60 days). If only the day is missing for either date or both dates, and the progression date and anticancer treatment end date corresponds to two consecutive months within the same year, then, the patient will be considered refractory, otherwise they will be considered not refractory.

Best overall response (BOR) is SD or PD.

Reason for treatment discontinuation is “progressive disease”.

- Prior transplant: patients with transplant, type of transplant, number of transplant by patient, time from last transplant to reference date (months).
- Prior surgery: patients with any prior surgery related to cancer, type of surgery and time from last surgery to reference date (months).
- Prior radiotherapy: number (%) of patients with any prior radiotherapy related to cancer, intent, and time from last radiotherapy to reference date (months).

Any technical details related to computation, dates, and imputation for missing dates, are described in [Section 2.5](#).

Vital signs

Vital signs include: heart rate, systolic and diastolic blood pressure, respiratory rate, temperature and weight.

Renal status

Creatinine clearance, ie, glomerular filtration rate (GFR) in mL/min/1.73 m² (qualitative variable: <15, [15-30[, [30-60[, [60-90[, ≥90) will be calculated from serum creatinine concentration measured at baseline using Modified Diet in Renal Disease (MDRD) formula ([Section 2.5.1](#)).

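### With a missing day, the SAP's refractory rule rejects same-month and December-January dates that meet its own 60-day definition

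*SAP*

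**What the plan says.** SAP 2.1.1 (Prior anti-myeloma therapies) derives refractory status for each main class of prior treatment and for the last prior treatment. The conditions are alternatives: "A patient is considered to be refractory if any of the following conditions are met". They are:

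- **Dates.** With complete dates, progression must be within "60 days of anticancer treatment end date", that is, progression date minus end date of at most 60 days. "If only the day is missing for either date or both dates", a month-level rule takes over: the patient is refractory if the pair "corresponds to two consecutive months within the same year, then, the patient will be considered refractory, otherwise they will be considered not refractory".
- **Response.** "Best overall response (BOR) is SD or PD".
- **Stop reason.** "Reason for treatment discontinuation is" progressive disease.

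The 60-day window agrees with Protocol Appendix F, which includes disease that "progresses within 60 days of last therapy". SAP Table 4 uses the derived status for four subgroups: refractory to IMiD, to PI, to both ("Refractory to IMiD and PI") and to daratumumab.

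**The concern.** The month-level rule stands in for the 60-day window when the exact gap is unknown. It should therefore accept month patterns that guarantee, or almost guarantee, a gap of at most 60 days. It accepts adjacent months within one year. Every other pattern is called not refractory, and that includes two patterns that belong on the refractory side:

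- **Same month.** These are not consecutive months, so they fail, although they give the shortest gaps possible.
- **December-January.** These are consecutive months but not in the same year, so they fail. The 60-day definition gives no reason to treat the turn of the year differently.

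The error has one direction: refractory patients move to the non-refractory group. The labels describe the population's resistance to each drug class and split the ORR and BOR summaries (SAP 2.4.4.1) and the PFS subgroups (SAP 2.1.3.2). With 35 patients per arm, one moved patient is 1/35 = 2.9% of an arm and a larger share of any subgroup.

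**Working it through.** **Inputs.** The 60-day window and the month-level rule come from SAP 2.1.1. The convention for other partial dates of disease characteristics (a missing day becomes day 1) comes from SAP 2.5.3. The documents do not give the distribution of gaps or the number of partial dates, so step 3 uses assumptions.

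**Step 1: the pattern the rule accepts.** All possible day pairs were enumerated for adjacent months within one year, comparing progression date minus end date with 60 days. In a non-leap year (2017), 10,136 of 10,137 pairs are within 60 days; in a leap year (2016), 10,198 of 10,199. The single exception in each year is 1 July to 31 August, 61 days. The rule is therefore sound where it says refractory.

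**Step 2: the two patterns it rejects.**

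| Pattern | Largest gap | Day pairs within 60 days | Label from the rule |
|---|---|---|---|
| Adjacent months, same year | 61 days | all but one | refractory |
| Same month | 30 days | all | not refractory |
| December-January | 61 days | 960 of 961 | not refractory |

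The one December-January exception is 1 December to 31 January, 61 days. That matches July-August, which the rule accepts.

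**Step 3: share of truly refractory pairs that fail, both days missing.** A simple version uses 30-day months and a gap d uniform on 0 to 60 days. The chance that both dates fall in one month is 1 - d/30 for d up to 30 and zero beyond, so

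P(same month) = (1/60) × ∫₀³⁰ (1 - d/30) dd = 15/60 = 25%.

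Exact calendar enumeration, with end dates uniform over four years, gives:

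| Assumed true gap | Same month | December-January | Total |
|---|---|---|---|
| Uniform on 0-60 days | 25.8% | 4.3% | 30.1% |
| Uniform on 0-30 days | 50.7% | 4.1% | 54.8% |

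December-January is one of the 12 adjacent-month pairs, so about 1/12 = 8.3% of adjacent-month cases are lost at the turn of the year.

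**Step 4: does SAP 2.5.3 repair it?** Setting both missing days to 1 gives a gap of 0 days for the same month and 31 days for December-January. Both are refractory, which is the opposite of the rule in 2.1.1. Section 2.5.3 thus conflicts with the specific rule and does not complete it.

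**The case against.** The strongest reply is that failing the date criterion does not settle a patient's final status. Any one condition is enough, and a patient who progressed in the month therapy ended will often have progression recorded as the stop reason. Final misclassification needs a partial date, a best response other than SD or PD, and a stop reason other than progression, such as toxicity or completion of planned therapy. SAP 2.5.3 also says that complete dates were sought, so partial dates should be a residual group. The number finally mislabelled cannot be estimated from the documents and could be zero.

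The consequences are also limited. The only hypothesis test is ORR by arm in the randomized population; the subgroup summaries are descriptive, and no secondary endpoint is tested. The rule uses history from before the study and applies equally to all arms, so it does not favour one by design. The overall study-entry classification (relapsed and refractory, primary refractory, relapse) is defined separately and without this rule.

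All of this stands, and it keeps the point minor. It does not make the rule right: for a responder who stopped for another reason and then progressed within 60 days, the dates are the only route to the correct label.

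Pairs two months apart are a different matter. About 47% to 55% of their day pairs are within 60 days, so they are truly ambiguous, and calling them not refractory is a defensible choice.

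**Conclusion.** The concern holds. As written, the month-level rule contradicts the SAP's 60-day definition in every same-month case and in 960 of 961 December-January day pairs. At the level of the date criterion, about 30% of truly refractory pairs with both days missing are rejected for these two reasons if gaps are uniform on 0 to 60 days, and about 55% if they are uniform on 0 to 30 days; both distributions are assumptions. The share finally mislabelled is smaller, because the response and stop-reason criteria recover some patients, and the number of patients is unknown. What is affected is the description of refractoriness by drug class and last regimen, and the four Table 4 subgroups. The primary ORR comparison is not affected. It is a small correction worth making.

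**What to change.** Replace the month-level condition in SAP 2.1.1 with: if only the day is missing for one or both dates, the patient is refractory when the two dates fall in the same calendar month or in two consecutive calendar months, including December-January. State that this overrides the day-1 convention in SAP 2.5.3 for this variable, so that the two sections no longer give opposite answers.

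The revised rule is right for every same-month pair and for all but one December-January pair, which matches the accuracy of the pattern already accepted. One further case can be settled in the same edit: the complete-date formula has no lower limit, so progression dated two or more months before treatment end also meets it, and the SAP should say how such a pair is classed when a day is missing.

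The cost is one or two sentences in the SAP and one line of code. No new data are needed.
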